SARS-CoV-2	Severe acute respiratory syndrome coronavirus 2
SOT	Solid Organ Transplant
WHO	World Health Organization

2. Introduction

2.1 Background and rationale

Although the impact of COVID-19 has been significantly reduced thanks to the effectiveness of vaccination and antiviral treatments, the risk of breakthrough infection remains higher in the immunocompromised population [1].

Immunocompromised patients are at increased risk for SARS-CoV-2-associated morbidity and mortality due to immunologic deficits that limit normal immune response and viral clearance [2-3]. Furthermore, the type of immunosuppression and the treatments performed significantly impact the natural trajectory of the COVID-19 infection, as in the case of patients with impaired adaptive humoral immunity who are relatively protected from acute infectious toxicity but have a high risk of prolonged viral shedding, viral rebound, and chronic infection [2-3].

In this group of patients, also known as “long persisters”, we find especially haematological patients with B cell malignancies or undergoing B cell targeting therapies such as anti-CD20 and CAR-T cell therapy. These patients, in addition to the complications related to SARS-CoV-2 infection itself, represent a particularly interesting population as the lack of viral clearance can lead to delays in life-saving treatments.

Despite major advances in our understanding of COVID-19, there is still a lack of consensus on how to define the condition of persistent infection in immunocompromised patients, also called “protracted SARS-CoV-2 infection” or “persistent inflammatory sero-negative COVID” [4-5]. In particular, two recent studies have tried to distinguish this phenomenon from “long COVID-19” and “post-COVID-19 condition”, which is defined by the WHO as a syndrome that occurs in individuals who have contracted COVID-19 in the previous 3 months and have at least 2 months of ongoing symptoms (such as fatigue, dyspnoea, and cognitive dysfunction), with no alternative diagnoses [6]. Both studies [4-5] suggest the use of diagnostic criteria that combine baseline host immunodeficiency, clinical signs and virological data, which we can summarize as follows:

- Host criterion: underlying immunosuppression such as HCT, CAR T-cell recipient, lymphoma or B-cell malignancy, SOT, Anti-CD20 therapy or other B/T cell targeted therapies, primary and acquired immunodeficiencies.
- Clinical criterion: persistent/relapsing symptoms (fever, dyspnea, hypoxemia) and/or persistent/relapsing changes on chest-X ray or CT scan after extensive negative infectious work up.
- Virological criterion: persistently positive SARS-CoV-2 PCR \geq 21 days.

Although 21 days may not be a particularly long duration in this type of patient, in this study we will use this time reference to identify patients with persistent infection.

Current COVID-19 treatment guidelines recommend the use of a single agent within few days of symptoms for all the patients with mild disease but with risk factors for progression

to severe disease, including immunocompromised condition. Remdesivir remains the only approved antiviral to treat hospitalized patients with COVID-19 in case of progression to LRTI and, in any case, after 10 days from diagnosis patients are no longer eligible for any treatment. Moreover, specific indications for immunocompromised patients are limited to the use of long-acting monoclonal antibodies as SARS-CoV-2 pre-exposure prophylaxis for individuals who may have an inadequate immune response to COVID-19 vaccination. It should also be specified that there is currently insufficient evidence to guide clinical recommendations for other treatments in immunocompromised patients [7].

However, in clinical practice, it appears clear that such recommendations are not sufficient to guarantee the cure of SARS-CoV-2 infection in immunocompromised patients, in particular in the “long persisters” population. Currently in literature, only case reports or small case series have described the prevalence and the management of patients with persisting infection. These studies show a wide variability of therapeutic approaches ranging from the adoption of repeated or prolonged cycles of remdesivir [8-10] or nirmatrelvir/ritonavir [11], dual antiviral therapy [12-13] and combination therapy with antiviral and monoclonal antibodies [14-16]. These case reports show variable success rates and highlight the need for larger studies focused on immunocompromised patients, to identify the best therapeutic approach in this population.

With this premise, we would like to conduct an observational study on immunocompromised patients, and specifically on haematological patients with B cell malignancies diagnosed with SARS-CoV-2 infection, with the aims of assessing the prevalence of those with persisting COVID-19, associated risk factors and describe the different clinical managements and their related outcomes.

2.2 Importance of the study and its clinical relevance

This study is part of the EU H2020 project “Connecting European Cohorts to Increase Common and Effective Response to SARS-CoV-2 Pandemic: ORCHESTRA” (Grant Agreement n. 101016167), which addresses task 4.6 “*Prevalence, risk factors and therapeutic management of persisting COVID-19 in fragile patients*”.

We deem that the results of our study could help improve the management of immunocompromised patients at risk for developing persisting COVID-19. Indeed, by describing the burden, host, risk factors, therapeutic management and outcome of immunocompromised patients with persisting COVID-19, we may inform future interventional studies and current clinical practice regarding a currently unmet need with controversial evidence.

3. Objectives of the study

3.1 Primary objective

The primary objective of this study is to describe the prevalence of SARS-CoV-2 persisting infection and the related risk factors in immunocompromised patients with B cell malignancies or undergoing B cell targeting therapies.

3.2 Secondary objectives

The secondary objective of the study is to describe and compare between patients with and without persisting COVID-19 the clinical, virological and radiological outcomes and the different therapeutic approaches performed.

3.3 Endpoints

The first primary endpoint variable will be the prevalence of persisting SARS-CoV-2 infection among the immunocompromised patients defined as the persistence or the recurrence of symptoms and signs (fever, dyspnea, hypoxemia, changes on chest-X ray or CT scan) and positive SARS-CoV-2 PCR ≥ 21 days after the time 0 (day of the first test positive for SARS-CoV2 infection).

The endpoints for the secondary objectives are:

- Duration of treatment carried out to address the persistent COVID-19 condition and treatment-related adverse effects.
- Duration of viral shedding, defined as the number of days between the first positive test and first negative PCR test.
- Duration of symptoms, defined as the number of days between symptoms onset and the clinical cure.
- Prevalence of imaging alterations, defined as the presence of new ground-glass and/or crazy paving and/or interstitial infiltrates at chest CT scan during the persisting infection (starting from 21 days after the first positive test until viral clearance).
- Re-infection within 120 days, define as new positive test with or without symptoms after viral clearance has been achieved.
- All-cause 120-day mortality.

4. Investigational plan

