4.8 Statistical Analysis Plan

Patients' characteristics will be summarized using absolute frequencies and percentages (categorical variables) and mean±standard deviation or median and interquartile range (scale variables, according to their distribution).

The prevalence of persisting SARS-CoV-2 infection among the immunocompromised patients will be obtained as the ratio of the number of patients with evidence of persisting SARS-CoV-2 infection on the total number of enrolled patients.

As for the analysis of risk factors for persisting COVID, comparisons between COVID-persistent and non-persistent patients will be carried out by means of survival analyses for all outcomes expressed as durations (time-to-event analyses). These outcomes will be compared by estimating Kaplan-Meier curves, calculating log-rank tests and multiple Cox regressions in which COVID persistence will be the main risk factor and including the confounders and effect modifiers listed below.

- Age
- Sex
- Comorbidities (Charlson Comorbidity Index)
- Underlying hematologic disease state
- Chemotherapy treatments performed
- Duration of Hospital stay
- Admissions to intensive care
- Days with central venous catheter
- Bacterial and fungal superinfections
- Vaccination status
- Previous SARS-CoV-2 infections
- Serological status (anti-SARS-CoV-2 antibodies)

Re-infection and imaging alterations rates will be calculated as the ratio of the number of events to the overall number of patients, and the comparison between persisters and non-persisters will be carried out by calculating the corresponding risk ratios. A multiple logistic regression model will assess the relationship between exposure and re-infection (image alteration) net of the potential confounders.

For secondary aims, the secondary endpoints will be described just for the patients with persisting COVID, categorical variables will be reported as number and relative

frequencies, continuous variables will be reported as mean±SD or median and IQR according with their distribution.

5. Administrative procedures and declarations

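### The plan promises to compare treatment approaches between persisters and non-persisters, but specifies no endpoint or analysis that can do so

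*Combined protocol and SAP*

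**What the plan says.** Section 2.1 closes with the aim to "describe the different clinical managements and their related outcomes". Section 3.2 turns this into a between-group objective: to "describe and compare between patients with and without persisting COVID-19 the clinical, virological and radiological outcomes and the different therapeutic approaches performed".

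Section 3.3 lists six endpoints for the secondary objectives. One concerns treatment: "Duration of treatment carried out to address the persistent COVID-19 condition and treatment-related adverse effects". The same section defines persistence by symptoms or signs together with a "positive SARS-CoV-2 PCR ≥ 21 days after the time 0".

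Section 4.8 gives two rules that bear on this endpoint. The first is that "comparisons between COVID-persistent and non-persistent patients will be carried out by means of survival analyses for all outcomes expressed as durations (time-to-event analyses"), using Kaplan-Meier curves, log-rank tests and Cox regression. The second is "For secondary aims, the secondary endpoints will be described just for the patients with persisting COVID". The only drug treatment in its list of confounders and effect modifiers is "Chemotherapy treatments performed".

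**The concern.** The objective and the endpoint do not fit together. The objective needs a treatment variable that exists in both groups. The endpoint is tied to a condition that defines one group and is absent from the other.

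It also measures a different attribute from the one the rationale calls unsettled. Section 2.1 describes variation in the kind of treatment: repeat or extended antiviral courses, two antivirals together, or an antiviral with a monoclonal antibody. A number of days cannot tell these apart.

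At stake is a stated secondary objective. An analyst who follows the text has three options: make no treatment comparison, contrast some days with none, or choose a treatment variable after seeing the data. The first leaves the objective unanswered, the second is true by construction, and the third is post hoc. COVID-19 therapy given early is also a plausible risk factor for persistence under the primary objective, and it appears in no endpoint and no listed model.

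**Working it through.** **The plan's own figures.** No figure is given for a treatment comparison. The only sizing in Section 4.4.3 is for 120-day mortality, and it reproduces. With allocation ratio k = 0.43 and survival 0.97 versus 0.93:

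- HR = ln(0.93)/ln(0.97) = 2.383
- Events (Freedman) = (1.960 + 0.842)² × (1 + 0.43 × 2.383)² / [0.43 × (1 − 2.383)²] = 39.1
- Event probability = (0.03 + 0.43 × 0.07)/1.43 = 0.04203
- N = 39.1/0.04203 ≈ 931, against 933 in the plan

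This supports the group sizes as planning figures and has no other bearing on the point.

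**Who can have a value.** Section 4.4.3 expects about 1,000 patients, of whom about 300 have prolonged infection. Non-persisters number 1,000 − 300 = 700, and 700/1,000 = 70%. None of them has the persistent condition, so none has a treatment for it. The 30% behind the 300 is an estimate from viral shedding beyond 21 days alone, whereas Section 3.3 also requires symptoms or signs. If that estimate holds, 70% is more likely a floor than a ceiling.

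**The sections side by side.**

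| Section | What it requires for treatment | Consequence |
|---|---|---|
| 3.2 | A comparison of approaches, persisters versus non-persisters | Needs a variable defined in both groups |
| 3.3 | Duration of, and adverse effects from, treatment of the persistent condition | Defined in persisters only; no agent, combination or course count |
| 4.8, rule on durations | All durations compared between groups | The non-persister group is empty or set to zero |
| 4.8, rule on secondary endpoints | Description in persisters only | The comparison promised in 3.2 is dropped |
| 4.8, covariates | Chemotherapy listed, no antiviral or monoclonal antibody | COVID-19 therapy enters no listed model |

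The two rules in Section 4.8 cannot both apply to treatment duration. The second also clashes with that section's own between-group risk ratios for re-infection and imaging, which are secondary endpoints too. Whichever rule is followed, the comparison in Section 3.2 is not obtained.

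**The case against.** The strongest reply is that the study is about persisters. Section 2.2 gives its task as the prevalence, risk factors and management of persisting COVID-19, and the approaches reviewed in Section 2.1 come from reports on persisting infection. On that view a treatment endpoint confined to persisters is deliberate, and under the second rule in Section 4.8 the contrast of some days with none would never be run. This justifies keeping the endpoint as a description. It does not remove the comparison in Section 3.2, nor the rule in Section 4.8 that compares all durations.

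A reader might infer more than the text supports, in three ways:

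- **That early treatment data are lost for all 1,000 patients, or collected only in persisters.** Section 4.7 says that a pre-established eCRF is used, but its fields are not in the documents. Sites may record therapy in everyone.
- **That therapy in days 0-20 is excluded by rule.** The imaging endpoint has an explicit window starting at day 21, but the treatment endpoint has none. How a course begun before day 21 and continued beyond it should be counted is undefined, which is different from excluded.
- **That success rates by approach will be biased by a known amount.** The documents give no figures for this, and Section 4.8 specifies no analysis of success by approach. Results in treated persisters and in all treated patients answer different questions.

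It can also be said that the adverse-effect half of the endpoint covers any treatment. As a single item, the more natural reading ties it to the same treatment. Even the wider reading would not supply a comparison of approaches.

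**Conclusion.** The point stands as a conflict between Sections 3.2, 3.3 and 4.8. With the endpoints and analyses as written, the comparison of therapeutic approaches between groups cannot be made. About 70% of the cohort has no defined value for the only treatment endpoint, and the type of therapy is not an endpoint in anyone. The claim goes no further than that; it does not say that the data are missing.

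The 70% rests on the plan's 300/700 split. The rest follows from the wording and needs no assumption about the results. One secondary objective is affected. The primary prevalence estimate and the mortality power calculation are not, and no change in sample size follows.

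**What to change.** 1. **Section 3.3.** Add an endpoint for every enrolled patient: SARS-CoV-2-directed therapy received from time 0 (agents, single or combined, number of courses, start and stop dates) and treatment-related adverse effects.
2. **Between-group comparison.** Base it on the proportion receiving each type of therapy started in days 0-20. Do not use total treatment days, which early clearance or death cuts short, so that the difference would again partly reflect how the groups are defined. Report patients who die before day 21 separately, because their persistence status cannot be classified.
3. **Treatment of the persistent condition.** Keep its duration as a description in persisters with no between-group test, and state how a course spanning day 21 is counted. Label any table of outcomes by approach as descriptive, since treatment start time and indication differ between approaches.
4. **Sections 4.8 and 3.2.** Exclude this duration from the all-durations comparison, limit the persisters-only sentence to this endpoint, and reword Section 3.2 to match.

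The cost is a wording amendment and, if the eCRF does not already hold these fields, some extra abstraction for non-persisters. Section 4.7 already names clinical charts and hospital electronic records as the data sources. The comparison remains observational and open to confounding by indication, so it should be reported as an association.

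### Viral shedding and imaging from day 21 are tested between groups that a day-21 PCR-and-signs rule itself defines, so both comparisons are circular; section 4.8 also contradicts itself on whether to compare

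*Combined protocol and SAP*

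**What the plan says.** All places are in the combined protocol and SAP.

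- **Group label (3.3).** Persisting infection is "defined as the persistence or the recurrence of symptoms and signs (fever, dyspnea, hypoxemia, changes on chest-X ray or CT scan"), together with a positive PCR at least 21 days after the first positive test (time 0).
- **Shedding endpoint (3.3).** "Duration of viral shedding, defined as the number of days between the first positive test and first negative PCR test".
- **Imaging endpoint (3.3).** "presence of new ground-glass and/or crazy paving and/or interstitial infiltrates at chest CT scan during the persisting infection". The window is stated there as "during the persisting infection (starting from 21 days after the first positive test until viral clearance").
- **Objective (3.2).** To "describe and compare between patients with and without persisting COVID-19 the clinical, virological and radiological outcomes".
- **Analysis (4.8).** Duration outcomes are compared between the two groups by Kaplan-Meier, log-rank and multiple Cox regression, with persistence as the main exposure. Imaging rates use all patients as denominator and are compared by risk ratio and logistic regression. No landmark or time-dependent coding of persistence is given.
- **Last paragraph of 4.8.** Secondary endpoints are to be described in persisters only.
- **Sample size (4.4.3).** The study is sized on a between-group log-rank test of 120-day mortality. The section ends by calling 1,000 patients fully sufficient for imaging because a bigger group difference is expected; it gives no rates.

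**The concern.** For shedding, a late positive PCR is an entry condition for one group. A patient who clears before day 21 and stays negative is a non-persister by rule. A persister without an earlier negative cannot reach the event before day 21. The test therefore largely measures the definition.

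For imaging, a patient who clears before day 21 has no window in which an event can count, yet stays in the denominator. A patient who is PCR-positive with CT changes inside the window generally becomes a persister, because CT changes are a qualifying sign. Both mechanisms push the risk ratio away from 1.

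The last paragraph of 4.8 adds a separate problem. One analyst could report between-group tests and another a description of persisters only, and both could cite 4.8. Read literally, that paragraph also removes the mortality comparison on which the sample size rests.

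At stake is the virological and radiological part of the objective in 3.2: an artefact of definition could be reported as a finding.

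**Working it through.** **1. The plan's own figure.** Freedman formula with ratio ψ = 0.43 and survival 0.97 vs 0.93:
- HR = ln 0.93 / ln 0.97 = 2.383.
- Events = (1.960 + 0.842)² × [(0.43 × 2.383 + 1)/(2.383 − 1)]² / 0.43 = 39.1, rounded up to 40.
- Event probability = 1 − (0.97 + 0.43 × 0.93)/1.43 = 0.0420.
- N = 39.14/0.04203 = 931, or 652 + 281 = 933 after rounding each group up. The plan states 933.

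All 17 legible rows with a stated N reproduce. The table concerns mortality only; the plan gives no figure for shedding or imaging.

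**2. Shedding with no true difference.** From 4.4.3: N = 1,000 and about 30% shedding past day 21 (PCR alone, without the clinical part). Assumed: one exponential clearance rate for everyone, and a share q of day-21 shedders with signs, independent of clearance.
- λ = −ln(0.30)/21 = 0.0573 per day.
- Persister median = 21 + ln 2/λ = 33.1 days.
- Non-persister median at q = 1 (700 patients, so the 350th of 1,000 to clear): −ln(0.65)/λ = 7.5 days.
- At q = 0.5 (850 patients, the 425th): −ln(0.575)/λ = 9.7 days.

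So medians of about 33 vs 8–10 days arise from a single clearance rate. Simulation (1,000 runs per row):

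| q | Persisters | Non-persisters still shedding at day 21 | Apparent HR for clearance (true 1.0) | Log-rank rejection |
|---|---|---|---|---|
| 1.0 | 300 | 0 | about 0 (complete separation) | 100% |
| 0.9 | 271 | 30 | 0.15 | 100% |
| 0.7 | 210 | 90 | 0.26 | 100% |
| 0.5 | 150 | 150 | 0.33 | 100% |

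A log-normal model (sigma 0.7, q from 25% to 100%, retest gaps averaging 0 to 14 days) also rejects in 100% of null runs. Median \|z\| runs from 29 down to 5.

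**3. Early-negative relapsers.** Under 3.3, a patient with an early negative PCR and a later positive one can be a persister with short recorded shedding. The documents give no share. In the log-normal model:
- 20% of persisters (q = 0.25 or 0.5): rejection 98–100%.
- 40%: mostly 90% or more, falling to about 60% at q = 0.25 with 14-day gaps.
- 60%, 14-day gaps, q of 0.5 or less: about 12–16%, with no fixed direction.
- 80%, with 14-day gaps, or 7-day gaps and q of 0.5 or less: the direction reverses in nearly all runs.

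**4. Imaging with equal CT risk.** Assumed: 30% of all patients have CT changes, 70% have other signs, clearance as in step 2, and PCR retests every 7 or 14 days. Because CT changes themselves qualify, the share among persisters is 0.30/(1 − 0.70 × 0.30) = 38%. Non-persisters contribute events only when the last positive falls before day 21 and the first negative after it.
- 7-day gap: 38.0% of 195 vs 4.48% of 805, risk ratio 8.5.
- 14-day gap: 38.1% of 164 vs 9.11% of 836, risk ratio 4.2.
- CT risk varied from 10% to 50%: 7.6–9.4 and 3.8–4.7.

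A second model, with a constant daily hazard of 1% or 3% from day 21 to the first negative PCR, gives median risk ratios of 2.9 to 69. If half or all infiltrates do not qualify a patient as a persister, the range is 2.4 to 24, with p < 0.05 in 82–100% of runs. The true ratio is 1 throughout.

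**The case against.** **Guaranteed result.** A reader might infer that the direction and significance of the shedding test are fixed in advance. The documents do not support that. Step 3 shows that both depend on the share of early-negative relapsers. The virological criterion in 2.1 speaks of a persistently positive PCR, which might exclude such patients, but 3.3 does not repeat it. What stands is circularity, not a certain result.

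**Empty imaging cell.** A reader might infer that non-persisters can have no imaging events by definition. That holds only if PCR status is known continuously and every CT change qualifies. Testing follows routine practice (4.3), so gaps can leave the window open. A first new infiltrate may be read as neither persistent nor recurrent. The clinical criterion in 2.1, "persistent/relapsing changes on chest-X ray or CT scan after extensive negative infectious work up", could also exclude an infiltrate explained by superinfection. The bias remains with non-persister events present.

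**Landmark as rescue.** Comparing patients still positive at day 21, with and without signs by then, keeps 4–6% error when both groups are retested equally often. Routine practice does not ensure that. With mean gaps of 5 vs 10 days null rejection is about 41–56%, and with 7 vs 14 days about 87–97%. Even at equal 7-day gaps, about 43% of patients with no negative PCR by day 21 have already cleared. Requiring a documented positive PCR still leaves 74–82%. The landmark is therefore not recommended.

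**Adjustment.** The log-rank and imaging tests simulated were unadjusted, and the adjusted Cox and logistic models were not run. The covariates in 4.8 do not, however, undo the use of the outcome in the label.

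**Already descriptive.** Under the last paragraph of 4.8, both endpoints are only described. That lowers the weight of the point, but the same section also orders the tests.

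**Conclusion.** The point holds as a matter of definition. The between-group tests of viral shedding and of imaging from day 21 are circular and cannot answer the comparative objective in 3.2. With no early-negative relapsers, the shedding test rejected in every simulated null run. The spurious imaging risk ratio ranged from 2.4 to 69. Apart from N = 1,000 and the 30% estimate, the inputs are assumptions, so these sizes are illustrative. The larger imaging difference expected in 4.4.3 is at least partly this artefact and cannot support the adequacy statement. The contradiction within 4.8, and between it and sections 3.2 and 4.4.3, needs no simulation.

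This should be fixed, but it concerns two secondary endpoints. A reader might infer that the prevalence estimate or the powered mortality comparison falls with them; this point does not show that. Re-infection is a separate matter. Describing "Duration of treatment carried out to address the persistent COVID-19 condition and treatment-related adverse effects" in persisters only is consistent with how that endpoint is defined.

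**What to change.** 1. In 4.8, remove the between-group log-rank, Cox, risk-ratio and logistic tests for viral shedding and for imaging from day 21.
2. Replace the last paragraph of 4.8 with: *Treatment duration, treatment-related adverse effects and imaging alterations from day 21 will be described in patients with persisting COVID-19; viral shedding will be described in both groups. No between-group test will be made for these endpoints.* The clause on summary statistics can stay. Re-infection and 120-day mortality keep their planned comparison.
3. Change 3.2 so that the comparison covers only the endpoints still compared, with shedding and imaging descriptive.
4. Report symptom duration descriptively, or label its comparison as partly determined by the group definition, since continuing symptoms are part of the label.
5. Delete the closing sentence of 4.4.3 on adequacy for imaging.

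**Cost.** No data beyond those already planned are needed. A stated secondary objective changes, so an amendment and Ethics Committee submission are required, and some secondary p-values are lost.
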